12.4.6.6 Suspected Drug-drug Interaction

If a drug-drug interaction associated with the IP is suspected, the investigator must forward the special situation worksheet to the sponsor by fax or email immediately (within 24 hours of awareness). Any associated (S)AEs are to be reported in the eCRF. If the AE meets the definition of an SAE, the SAE is also to be reported as described in [Appendix 12.4.5 Reporting Procedures for Serious Adverse Events] together with details of the suspected drug-drug interaction.

12.5 Liver Safety Monitoring and Assessment

The purpose of this appendix is to provide guidance for the monitoring of DILI during the course of the study. It should be noted that this section does not specify the end of study analyses of liver enzymes. The end of study liver enzymes analyses will be described in the SAP. Any subject enrolled in a study with active drug therapy and who reveals an increase of serum aminotransferases (AT) to $> 3 \times \text{ULN}$ (to $> 5 \times \text{ULN}$ in subjects with liver metastases) or TBL $> 2 \times \text{ULN}$ should undergo detailed testing for liver enzymes (including at least alkaline phosphatase [ALP], ALT, AST and TBL). Testing should be repeated within 72 hours of notification of the test results. For studies for which a central laboratory is used, alerts will be generated by the central laboratory regarding moderate and severe liver abnormality to inform the investigator and study team. Subjects should be asked if they have any symptoms suggestive of hepatobiliary dysfunction.

Definition of Liver Abnormalities

Confirmed abnormalities will be characterized as moderate and severe where ULN is as shown in [Table 12](#).

Table 12 Moderate and Severe Liver Abnormalities

	ALT or AST		Total Bilirubin
Moderate	$> 3 \times \text{ULN}$ (in patients without liver metastases), $> 5 \times \text{ULN}$ (in patients with liver metastases)	or	$> 2 \times \text{ULN}$
Severe	$> 3 \times \text{ULN}$	and†	$> 2 \times \text{ULN}$

ALT: alanine aminotransferase; AST: aspartate aminotransferase; ULN: upper limit of normal

†Samples taken simultaneously or within a maximum of 24 hours.

In addition, the subject should be considered to have severe hepatic abnormalities for any of the following:

- ALT or AST $> 8 \times \text{ULN}$
- ALT or AST $> 5 \times \text{ULN}$ for more than 2 weeks (in the absence of liver metastases)
- ALT or AST $> 3 \times \text{ULN}$ and† TBL $> 2 \times \text{ULN}$ or INR > 1.5 (If INR testing is applicable/evaluated)
- ALT or AST $> 3 \times \text{ULN}$ with the appearance of fatigue, nausea, vomiting, right upper quadrant pain or tenderness, fever, rash and/or eosinophilia ($> 5\%$)

The investigator may determine that abnormal liver function results, other than those described above, may qualify as moderate or severe abnormalities and require additional monitoring and follow-up.

Follow-up Procedures

Confirmed moderate and severe abnormalities in hepatic functions should be thoroughly characterized by obtaining appropriate expert consultations, detailed pertinent history, physical examination and clinical laboratory tests. The study site personnel are to complete the liver abnormality case report form (LA-CRF). Subjects with confirmed abnormal LFTs should be followed as described below.

Confirmed moderately abnormal LFTs should be repeated 2 to 3 times weekly then weekly or less if abnormalities stabilize or the IP has been discontinued and the subject is asymptomatic.

Severe hepatic liver function abnormalities as defined above, in the absence of another etiology may be considered an important medical event and may be reported as an SAE. The sponsor should be contacted and informed of all subjects for whom severe hepatic liver function abnormalities possibly attributable to IP are observed.

To further assess abnormal hepatic laboratory findings, the investigator is expected to:

- Obtain a more detailed history of symptoms and prior or concurrent diseases. Symptoms and new-onset diseases are to be recorded as “AEs” in the eCRF. Illnesses and conditions such as hypotensive events and decompensated cardiac disease that may lead to secondary liver abnormalities should be noted. Nonalcoholic steatohepatitis is seen in obese hyperlipoproteinemic and/or diabetic patients and may be associated with fluctuating AT levels. The investigator should ensure that the medical history form captures any illness that predates study enrollment that may be relevant in assessing hepatic function.
- Obtain a history of concomitant drug use (including nonprescription medication, complementary and alternative medications), alcohol use, recreational drug use and special diets. Medications, including dose, are to be entered in the eCRF. Information on alcohol, other substance use and diet should be entered on the LA-CRF or an appropriate document.
- Obtain a history of exposure to environmental chemical agents.
- Based on the subject’s history, other testing may be appropriate including:
 - Acute viral hepatitis (A, B, C, D, E or other infectious agents)
 - Ultrasound or other imaging to assess biliary tract disease
 - Other clinical laboratory tests including INR, direct bilirubin
- Consider gastroenterology or hepatology consultations.
- Submit results for any additional testing and possible etiology on the LA-CRF or an appropriate document.

Study Treatment Discontinuation

In the absence of an explanation for increased LFTs, such as viral hepatitis, preexisting or acute liver disease, presence of liver metastases, or exposure to other agents associated with liver injury, the subject may be discontinued from study treatment. The investigator may determine that it is not in the subject’s best interest to continue study treatment.

Discontinuation of study treatment should be considered if:

- AST or ALT $> 8 \times$ ULN
- AST or ALT $> 5 \times$ ULN for more than 2 weeks
- ALT or AST $> 3 \times$ ULN and† TBL $> 2 \times$ ULN or INR > 1.5) (if INR testing is applicable/evaluated)
- ALT or AST $> 3 \times$ ULN with the appearance of fatigue, nausea, vomiting, right upper quadrant pain or tenderness, fever, rash and/or eosinophilia ($> 5\%$)

† Samples taken simultaneously or within a maximum of 24 hours.

In addition, if close monitoring for a subject with moderate or severe hepatic laboratory tests is not possible, study treatment should be discontinued.

Hy's Law Definition:

1. Evidence that a drug can cause hepatocellular-type injury, generally shown by a higher rate than control of people with $3 \times$ AT elevations over the ULN ($2 \times$ elevations are too common in treated and untreated patients to be discriminating).
2. Cases of increased bilirubin (to at least $2 \times$ ULN) in people with concomitant AT elevation to at least $3 \times$ ULN (but it is almost invariably higher) and no evidence of intra- or extra-hepatic bilirubin obstruction (elevated ALP) or Gilbert's syndrome [Temple, 2006].

FDA Guidance for Industry titled "Drug-induced Liver Injury: Premarketing Clinical Evaluation" issued by the FDA on July 2009:

FDA Guidance for Industry:

1. The drug causes hepatocellular injury, generally shown by a higher incidence of 3-fold or greater elevations above the ULN of ALT or AST than the (nonhepatotoxic) control drug or placebo.
2. Among subjects showing such AT elevations, often with AT levels much greater than $3 \times$ ULN, 1 or more also show elevation of serum TBL to $> 2 \times$ ULN, without initial findings of cholestasis (elevated serum ALP).
3. No other reason can be found to explain the combination of increased AT and TBL, such as viral Hepatitis A, B or C; preexisting or acute liver disease; or another drug capable of causing the observed injury.

Reference

Temple R. Hy's Law: Predicting Serious Hepatotoxicity. *Pharmacoepidemiol Drug Saf.* 2006; 15(4):241-3.

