4.1.4 Dose Limiting Toxicity Criteria

A DLT is defined as any of the following AEs (graded using National Cancer Institute Common Terminology Criteria for Adverse Events [NCI-CTCAE] Version 4.03) that the investigator (or sponsor) cannot clearly attribute to a cause other than IP:

- Grade 4 neutropenia or Grade \geq 3 febrile neutropenia
- Grade 4 thrombocytopenia or Grade 3 thrombocytopenia accompanied by bleeding that requires any transfusion
- Grade 4 anemia or Grade 3 anemia requiring transfusion
- Grade \geq 3 nonhematological AE (excluding asymptomatic changes to amylase, lipase and hypophosphatemia)
- Grade \geq 2 pneumonitis

- Aspartate aminotransferase (AST) or alanine aminotransferase (ALT) > 5 × upper limit of normal (ULN; Grade ≥ 3) in subjects without liver metastases
- AST or ALT > 8 × ULN in subjects with liver metastases
- AST or ALT > 3 × ULN and total bilirubin (TBL) > 2 × ULN (in subject with Gilbert's syndrome: AST or ALT > 3 x ULN and direct bilirubin > 1.5 x ULN)
- TBL > 3 × ULN (Grade ≥ 3)
- Grade ≥ 2 encephalopathy, meningitis or Grade ≥ 2 motor or sensory neuropathy
- Grade ≥ 2 pulmonary or central nervous system (CNS) hemorrhage
- Grade ≥ 3 hemorrhage
- Any grade arterial thrombotic event (angina, myocardial infarction, transient ischemic attack [TIA], cerebrovascular accident [CVA] and any other arterial thromboembolic event)
- Any grade gastrointestinal perforation
- Any grade wound dehiscence
- Guillain-Barré syndrome or myasthenic syndrome/myasthenia gravis
- IRR that requires the infusion to be discontinued

Febrile neutropenia, thrombocytopenia accompanied by bleeding that requires any transfusion, and anemia requiring transfusion regardless of grade, may be considered DLTs by the investigator (or sponsor). In addition, in case the second and/or third dose for Dose level A and Dose level B, or the second dose for Dose level C cannot be performed within 7 days after a scheduled visit for drug related toxicities not specified in the above bullet list, this may be also considered DLTs by the investigator (or sponsor).

Subjects who are tolerating IP at a dose level that is being reviewed due to the occurrence of DLTs in another subject will not be automatically precluded from continued dosing during the safety review, and will be allowed to continue dosing for as long as tolerated unless directed otherwise as a result of the safety review by the DESC.

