Creatinine	Either a) \leq institutional ULN, or b) $\text{eGFR}^* \geq 45 \text{ mL/min/1.73m}^2$ if creatinine is $>$ ULN *Using the Chronic Kidney Disease-Epidemiology Collaboration (CKD-EPI) creatinine equation (2009); online calculator: https://www.kidney.org/professionals/kdoqi/gfr_calculator
Hepatic	
Total bilirubin	Either: a) $\leq 1.5 \times \text{ULN}$, or b) Direct bilirubin $\leq \text{ULN}$ and TBL $< 3 \times \text{ULN}$ (for subjects with Gilbert's syndrome)
AST and ALT	$\leq 2.5 \times \text{ULN}$
Coagulation	
INR	Either: a) $\leq 1.5 \times \text{ULN}$ for subjects not receiving anticoagulants, or b) within desired therapeutic range for subjects receiving anticoagulants
aPTT	Either: a) $\leq 1.5 \times \text{ULN}$ for subjects not receiving anticoagulants, or b) within desired therapeutic range for subjects receiving anticoagulants

ALT: alanine aminotransferase; ANC: absolute neutrophil count; aPTT: activated partial thromboplastin time; AST: aspartate aminotransferase; eGFR: estimated glomerular filtration rate; INR: international normalized ratio; TBL: total bilirubin; ULN: upper limit of normal

9. Female subject is not pregnant (see [Appendix 12.3 Contraception Requirements]) and at least 1 of the following conditions apply:
 - Not a woman of childbearing potential (WOCBP; see [Appendix 12.3 Contraception Requirements])
 - WOCBP who agrees to follow the contraceptive guidance (see [Appendix 12.3 Contraception Requirements]) from the time of informed consent throughout the treatment period and for at least 6 months after the final study treatment administration.
10. Female subject must agree not to breastfeed starting at Screening and throughout the study period, and for 6 months after the final study treatment administration.
11. Female subject must not donate ova starting at first dose of IP and throughout the study period, and for 6 months after the final study treatment administration.

12. Male subject with female partner(s) of childbearing potential (including breastfeeding partner) must agree to use contraception (see [Appendix 12.3 Contraception Requirements]) throughout the treatment period and for at least 6 months after the final study treatment administration.
13. Male subject must not donate sperm during the treatment period and for 6 months after the final study treatment administration.

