6.7.1 Toxicities Requiring Permanent Discontinuation of ASP1948 Treatment

ASP1948 treatment will be permanently discontinued for the following toxicities that are assessed as related to ASP1948, if there is a reasonable possibility that the event may have been caused by ASP1948:

- Hematological toxicity requiring ASP1948 treatment interruption that does not recover to Grade 0 or 1 within 4 weeks
- AST or ALT $> 5 \times$ ULN (Grade ≥ 3) in subjects without liver metastases
- AST or ALT $> 8 \times$ ULN in subjects with liver metastases
- AST or ALT $> 3 \times$ ULN and TBL $> 2 \times$ ULN (in subject with Gilbert's syndrome: AST or ALT $> 3 \times$ ULN and direct bilirubin $> 1.5 \times$ ULN)
- TBL $> 3 \times$ ULN
- Grade ≥ 3 nonhematological AE except for Grade 3 rash that has improved to Grade 0 or 1 or Grade ≥ 3 endocrinopathies that are managed to Grade 0 or 1 with replacement therapy.
- Persistent Grade ≥ 2 AEs requiring ASP1948 interruption that do not recover to Grade 0 or 1 within 12 weeks after the last dose with steroid treatment tapered to physiological replacement doses (≤ 10 mg prednisone or equivalent) of study treatment. However, subjects with a persistent Grade ≥ 2 AE requiring ASP1948 interruption may continue on study treatment if asymptomatic and controlled, with investigator and sponsor agreement
- Grade ≥ 2 pneumonitis
- Guillain-Barré syndrome or myasthenic syndrome/myasthenia gravis
- Grade ≥ 2 encephalopathy, meningitis or Grade ≥ 2 motor or sensory neuropathy
- Any toxicity that results in the inability to reduce corticosteroid dose to 10 mg or less of prednisone or equivalent per day within 12 weeks
- Grade 3 or 4 IRRs

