6.7.2 Toxicities Requiring ASP1948 Treatment Interruption

ASP1948 treatment will be withheld for the following toxicities if there is a reasonable possibility that the event may have been caused by ASP1948:

- Grade 4 neutropenia or Grade ≥ 3 febrile neutropenia
- Grade 4 thrombocytopenia or Grade 3 thrombocytopenia accompanied by bleeding that requires any transfusion
- Grade 4 anemia or Grade 3 anemia requiring transfusion
- Grade 3 rash or Grade 3 endocrinopathies

- AST or ALT ≥ 3.0 and $\leq 5.0 \times \text{ULN}$ or TBL > 1.5 and $\leq 3 \times \text{ULN}$ (in subject with Gilbert's syndrome: AST or ALT ≥ 3.0 and $\leq 5.0 \times \text{ULN}$ or direct bilirubin $> \text{ULN}$) in subjects without liver metastases
- AST or ALT ≥ 3.0 and $\leq 8.0 \times \text{ULN}$ or TBL > 1.5 and $\leq 3 \times \text{ULN}$ (in subjects with Gilbert's syndrome: AST or ALT ≥ 5.0 and $\leq 8.0 \times \text{ULN}$ or direct bilirubin $> \text{ULN}$) in subjects with liver metastases
- Any Grade 2 or higher irAE (including but not limited to those listed below):
 - colitis or diarrhea
 - hypophysitis
 - adrenal insufficiency
 - nephritis
 - ocular inflammatory toxicity
 - pancreatitis
 - new-onset neurological symptoms or signs (other than Grade 2 or higher encephalopathy, meningitis or Grade 2 or higher motor or sensory neuropathy, which require permanent discontinuation of ASP1948 treatment)
 - IRR

Additionally, ASP1948 treatment may be interrupted for any AE, laboratory abnormality or intercurrent illness that in the judgment of the investigator warrants delaying dosing of ASP1948.

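### Appendix 12.5's combined ALT/bilirubin criterion for a severe liver abnormality lacks the Gilbert's syndrome rule used in Sections 4.1.4 and 6.7.1, so the two can disagree in either direction

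*Protocol*

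**What the plan says.** **Entry.** Section 5.1, criterion 8, has a separate bilirubin limit "for subjects with Gilbert's syndrome": direct bilirubin no higher than ULN and TBL below 3 x ULN. AST and ALT may be up to 2.5 x ULN.

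**Decision rules.** The combined liver rule in Section 4.1.4 carries a substitution: "in subject with Gilbert's syndrome: AST or ALT > 3 x ULN and direct bilirubin > 1.5 x ULN". Section 6.7.1 has the same one, opening "in subject with Gilbert's syndrome". The liver bullets of Section 6.7.2 also have a Gilbert's version based on direct bilirubin. For subjects with liver metastases it begins "in subjects with Gilbert's syndrome: AST or ALT" and starts at 5.0 x ULN.

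**Appendix 12.5.** The Table 12 Severe row requires ALT or AST above 3 x ULN with TBL above 2 x ULN. The list introduced by "the subject should be considered to have severe hepatic abnormalities for any of the following" repeats the combination and adds an INR limb. The list under "Discontinuation of study treatment should be considered if" uses it again. None of the three has a Gilbert's alternative. Within the appendix the syndrome appears only in the printed Hy's Law definition, which requires "no evidence of intra- or extra-hepatic bilirubin obstruction (elevated ALP) or Gilbert's syndrome". That definition is not linked to Table 12 or to either list.

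**The concern.** For a Gilbert's subject admitted with TBL above 2 x ULN, the bilirubin half of the severe criterion is met before the first dose and says nothing about the drug. A moderate ALT rise then completes the criterion.

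The severe class has these consequences:

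- Appendix 12.5, follow-up procedures: the sponsor is to be contacted if the abnormality is possibly attributable to the drug, and an SAE report is permitted.
- Appendix 12.5, discontinuation list: stopping treatment is to be considered.
- Section 12.4.1.2: transaminase values with TBL elevations that meet the 12.5 criteria, absent other causes of liver injury, are potential Hy's Law cases. They always count as important medical events and go through Section 12.4.5, which means within 24 hours.

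Gilbert's explains the bilirubin but not the ALT rise, so the proviso about other causes does not clearly exempt the subject. On a plain reading, Section 12.4.1.2 can label as potential Hy's Law a case that the definition in Appendix 12.5 excludes.

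**Working it through.** The protocol gives no figure to reproduce. The check applies the written thresholds to three Gilbert's subjects. All values are multiples of ULN.

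Inputs:

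- Entry (5.1): direct bilirubin at most 1, TBL below 3, ALT/AST at most 2.5.
- Combined rule, Gilbert's (4.1.4, 6.7.1): ALT/AST > 3 and direct > 1.5.
- Standalone rules (4.1.4, 6.7.1): ALT/AST > 5 without liver metastases or > 8 with them; TBL > 3, with no Gilbert's exception.
- Withholding, Gilbert's (6.7.2): ALT/AST 3.0 to 5.0 without metastases or 5.0 to 8.0 with them; or direct > 1.
- Appendix 12.5 Moderate: ALT/AST > 3 without metastases or > 5 with them; or TBL > 2.
- Appendix 12.5 Severe, combined: ALT/AST > 3 and TBL > 2.

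Cases A and B are eligible at entry with TBL 2.5, direct 0.9 and ALT 2.0. Only ALT changes on treatment. Case C is an on-treatment state. No subject has symptoms or a raised INR.

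| | A: no metastases | B: metastases | C: metastases |
|---|---|---|---|
| TBL / direct / ALT | 2.5 / 0.9 / 3.5 | 2.5 / 0.9 / 3.5 | 1.8 / 1.6 / 3.5 |
| Combined DLT and stop rule | not met (0.9 ≤ 1.5) | not met (0.9 ≤ 1.5) | met (3.5 > 3; 1.6 > 1.5) |
| Standalone ALT/AST rule | not met (3.5 ≤ 5) | not met (3.5 ≤ 8) | not met (3.5 ≤ 8) |
| Standalone TBL rule | not met | not met | not met |
| 6.7.2 liver bullet, if possibly related | withhold | not met (3.5 < 5.0) | met through direct bilirubin |
| 12.5 Moderate | yes | yes, through TBL | no (3.5 ≤ 5; 1.8 ≤ 2) |
| 12.5 Severe, combined | **yes** | **yes** | **no** |
| 12.5 Severe with the Gilbert's wording added | no | no | yes |

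In A and B the appendix says severe where the combined decision rules are not met. In C the combined DLT rule is met, and the permanent stop too if the event is related, yet the appendix assigns no class on those values.

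**Where they disagree, for TBL above 2 and below 3 with direct at most 1.** Without metastases the band is ALT/AST > 3 to ≤ 5, because above 5 ALT/AST alone is a DLT and a stop. With metastases the sharpest band is > 3 to < 5, where the 6.7.2 Gilbert's bullet does not require withholding.

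**Change needed to cross each line** (the rise must slightly exceed the figure where the threshold is strict):

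- ALT/AST from 2.5: (3.0 − 2.5)/2.5 = 20%. From 1.0: (3.0 − 1.0)/1.0 = 200%.
- Bilirubin under 12.5: none. Direct bilirubin under the combined rule, from 1.0: (1.5 − 1.0)/1.0 = 50%.
- TBL under the standalone rule, from 2.5: (3.0 − 2.5)/2.5 = 20%. From 2.9: (3.0 − 2.9)/2.9 = 3.4%.

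**The case against.** The best defence is that Appendix 12.5 is a monitoring net and calls itself guidance. An alert threshold may differ from a stopping threshold, and the two sets already differ elsewhere: without liver metastases, Section 6.7.1 stops at once above 5 x ULN, while the appendix considers stopping after more than 2 weeks above 5 x ULN. Extra alertness to an ALT rise is also reasonable, since Study 1948-CL-0101 reported a fatal hepatic failure judged related. This holds for cases A and B as a matter of caution. It does not explain case C, where the appendix is the less sensitive of the two.

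Second, the consequences are qualified. Sponsor contact depends on possible attribution, the SAE clause is permissive and requires no other etiology, and discontinuation is only to be considered when the raised tests lack an explanation, with liver metastases named as one. Without metastases, Section 6.7.2 already withholds drug from ALT/AST 3.0 x ULN if possibly related. All of this stands and keeps the point small.

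Third, Section 12.4.1.2 can be read together with the whole of Appendix 12.5, including the definition that excludes Gilbert's. That reading is possible, but the text does not direct the reader to it.

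Three stronger inferences are tempting and are not supported:

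- A reader might infer that the decision rules abandon total bilirubin in Gilbert's subjects. They do not: the standalone TBL > 3 x ULN rule in Sections 4.1.4 and 6.7.1 still applies to them.
- A reader might infer that all of Table 12 should move to direct bilirubin. With TBL 3.5, direct 1.2 and ALT 2.0 x ULN, a subject would then be a permanent stop if related, yet not even moderate, and would lose the moderate-class work-up.
- A reader might infer that the INR limb needs an anticoagulant exception, because Section 5.1 admits INR "within desired therapeutic range for subjects receiving anticoagulants". Section 12.4.1.2 does not cover INR, and the remaining consequences already leave room for investigator judgment.

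**Conclusion.** The inconsistency is real and minor. The combined severe criterion in Appendix 12.5 omits a substitution that the sponsor chose to make in Sections 4.1.4 and 6.7.1. It can over-classify a Gilbert's subject whose bilirubin has not changed, and it can miss one whose direct bilirubin has risen.

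A reader might infer that DLT counts or dose decisions are distorted. They are not: DLTs are defined in Section 4.1.4 and do not draw on Appendix 12.5. Nor does the work-up change in cases A and B, since TBL above 2 x ULN is already moderate. What changes is the class, sponsor contact, the discontinuation prompt and, on the plain reading of Section 12.4.1.2, a 24-hour report.

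The protocol does not say whether any Gilbert's subject was enrolled. With about 18 subjects planned and at most 27 evaluable, the number affected is few or none. In subjects with liver metastases, the metastases may count as another cause, which could reduce the effect to the class and sponsor contact. The 24-hour reporting consequence assumes that Gilbert's is not itself taken as another cause of liver injury.

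**What to change.** In the Table 12 Severe row, and in the combined bullet of the severe list and of the discontinuation list, add: *(in subjects with Gilbert's syndrome: ALT or AST > 3 x ULN and direct bilirubin > 1.5 x ULN)*, in place of the TBL limb for those subjects. Keep TBL > 2 x ULN in the Moderate row and in the opening testing trigger. Keep every other severe criterion, including the INR limb.

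Optionally, bracket the bullet as *ALT or AST > 3 x ULN and (TBL > 2 x ULN or INR > 1.5)*, since its run of and/or can be read two ways.

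The cost is wording in one appendix. Table 13 lists direct bilirubin only if available, but Sections 5.1, 4.1.4, 6.7.1 and 6.7.2 already depend on it in these subjects, so no test or visit is added. The downside is slightly fewer severe alerts in Gilbert's subjects. Subjects like A and B remain moderate and are still worked up. A subject like C becomes severe, though the values would still not set off the opening repeat-test trigger.
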